4.2 Study Milestones

A 7 year budget and recruitment plan have been created; key study milestones below.

STUDY MILESTONES

Pre-enrollment Study Initiation	9 months
Recruitment and Follow-up	90 months
Completion of Follow-up	3 months
Data Analysis and Publication	6 months
Total Duration	108 months

4.3 Organizational Structure and Communication Flow

[figure not shown]
The trial management is a partnership of the UCSF Clinical Coordinating Center (UCSF CCC) based in the Stroke Sciences Group (SSG), the NINDS NETT Network, which will be responsible for data management and oversight of NETT sites, and the POINT CRC, which will manage the non-NETT sites, including the sites outside the United States. Details of the trial leadership, management, and communications are provided in the Manual of Procedures.

The UCSF SSG involves 30 faculty and staff with expertise in study design, epidemiology, biostatistics, nursing, and study coordination. It has coordinated multicenter observational studies and clinical trials for the last decade.

As a trial of a neurological emergency, POINT is well suited for involvement of the NETT. Most subjects will likely be identified in the emergency department. The NETT includes 17 “Hub” institutions, each with approximately three “Spoke” hospitals that work together to recruit patients into simple trials of acute neurological diseases.

POINT is well suited for CRC physicians due to its simple design and compelling question that should attract a wide breadth of neurologists treating acute stroke in the community. The CRC has over 1,100 physicians registered from 47 states. Use of central basic research training and a central Institutional Review Board (IRB) facilitates research participation of physicians who practice in a community setting. The CRC has experience activating sites over a short period of time.

Point Trial Organization

4.3.1 Trial Organization

The trial will be directed by the Principal Investigator, who will have ultimate responsibility for all activities and products of the trial, and will oversee all functions. The Co-Principal Investigator will assist with trial oversight and will substitute for the PI as necessary. The trial will take advantage of the proven skills of three major entities: the UCSF CCC, the NINDS NETT Network, and the POINT CRC.

The NINDS NETT, through its Statistical and Data Management Center (SDMC), will provide statistical support and data management services, including reports to the DSMB and Clinician Event Coordinator, and shielding the UCSF CCC, NETT-CCC and POINT CRC from access to unblinded data during the performance of the trial. The Director of the NETT SDMC will be responsible for the randomization protocol, final statistical analysis plan and final data analysis.

The Operations Committee (OC), chaired by the Principal Investigator, will oversee the entire performance of the trial. The OC will meet every week, with members outside San Francisco joining by teleconference. Membership of the OC is provided in the Manual of Procedures.

Sanofi has agreed to contribute clopidogrel and its placebo at no cost and with no restrictions through May 2016. From May 2016 forward, additional supplies of study drug will be provided by Sharp Clinical Services, Inc.

4.4 Site Training, Certification, and Update

Both the NETT and the CRC have already provided training to their sites in Good Clinical Practice Guidelines and in some outcome assessments (e.g., NIHSS, modified Rankin Scale). Online modules for training new sites are also available.

Prior to initiation of subject enrollment, Site Investigators and Coordinators will complete online training programs and their certifications. In these training modules, the subject selection criteria and follow-up procedures will be reviewed. Case studies illustrating potential problems in adhering to study protocol and blinding will be discussed.

All investigators must complete the following training modules, and receive certification:

- Study procedures
- Primer on the diagnosis of TIA and its mimics
- Use of the ABCD² score
- POINT eligibility
- Modified Rankin Scale
- NIHSS

Successful completion of the training program and confirmation of approval from the local Institutional Review Board for human research will be required before a site is certified to enroll subjects. Web-based meetings, with the PI and key staff available to address questions, will occur intermittently. Certification of competence will be obtainable on the Web.

A detailed Manual of Procedures will serve as the primary document describing all study related procedures. It will serve as a guide for training of clinical site personnel and will be updated periodically throughout the study, as needed. A system will be implemented for the clinical sites to call

or e-mail any procedural questions regarding the study. The UCSF CCC will formulate answers in consultation with the Operations Committee, and will periodically distribute to the participating centers a set of frequently asked questions (FAQ) and answers. These questions and answers will also be available on the POINT Resources and Training page under FAQs and can be searched by topic. Intermittently, the answers to questions will be incorporated into Manual of Procedures revisions.

The NETT will manage and conduct site visits for its sites and the CRC will manage and conduct site visits for the non-NETT sites. Each site will be visited at least once during the trial, and as needed if questions about data quality or problems with recruitment arise, or there is a concern about noncompliance requiring specific or systemic corrective actions.

4.5 Contact Schedule and Measurements

Subject encounters will include screening, randomization, telephone follow-up, and a final telephone or in-person visit. In addition, event visits are to occur whenever subject contact suggests that possible stroke, TIA or MI may have occurred. Stroke and TIA events can be evaluated via telemedicine when necessary. Event visits for MI may be conducted over the telephone. Event visits are conducted as needed and can be done more than once for the same subject. Measurements to be taken at these encounters are listed in Section 1.2, Schedule of Activities and Assessments. Details of the visits are provided in the Study Procedures section (Section 9).

Refer to the Manual of Procedures and Data Collection Guidelines for more specific details on how/when to submit Case Report Forms for events.

4.6 Outcomes

The primary outcome of the trial is a composite outcome: ischemic stroke, myocardial infarction, and ischemic vascular death. The primary safety outcome is major hemorrhage. Additional efficacy and safety outcomes also will be assessed. All components of the primary and safety outcomes will be adjudicated.

4.6.1 Definitions of Clinical Outcomes/Serious Adverse Events

Ischemic stroke: An acute focal infarction of the brain or retina (and does not include anterior ischemic optic neuropathy (AION)).

Criteria:

- 1) Rapid onset of a new focal neurological deficit with clinical or imaging evidence of infarction and not attributable to a non-ischemic etiology (not associated with brain infection, trauma, tumor, seizure, severe metabolic disease, or degenerative neurological disease); or
- 2) Rapid worsening of an existing focal neurological deficit that is judged by the Investigator to be attributable to a new infarction. Criteria for symptoms attributable to new infarction *may* include symptoms that persist and are judged by the investigator to be attributable to new infarction, imaging evidence of infarction, or no evidence of a non-ischemic etiology.

TIA: A neurological deficit of sudden onset, resolving completely, attributed to focal brain or retinal ischemia without evidence of associated acute focal infarction of the brain.

Criteria: Rapid onset of a focal neurological deficit that is without evidence of acute focal infarction of the brain, and is not attributable to a non-ischemic etiology (brain infection, trauma, tumor, seizure, severe metabolic disease, or degenerative neurological disease).

Symptomatic hemorrhagic transformation of an ischemic stroke: Any extravascular blood within an area of known acute/subacute infarction which is judged to be nontraumatic, and responsible for neurologic symptoms. To be considered symptomatic, the hemorrhagic transformation must be judged to be partially responsible for the subject's clinical neurologic presentation (i.e., the area of infarction is not adequate to explain the neurologic deficit, or a secondary neurologic deterioration occurred corresponding to the timing of hemorrhagic transformation.)

Criteria (must meet both of the following):

- 1) Imaging evidence (by CT or MR) of extravascular blood within the area of infarction.
- 2) Symptoms judged to be related to the hemorrhagic transformation. Scenarios which may be judged as symptomatic: (i), If blood is already present on imaging at presentation, symptoms are out of proportion to what would be expected for the size and location of the infarct at presentation; (ii) Clinical deterioration, defined by an increase of 4 points or more in the score on the NIHSS or leading to death, occurring after the initial ischemic event, and identified as the result of the hemorrhagic transformation; or (iii) Mass effect secondary to the hemorrhagic transformation causing symptoms.

Asymptomatic hemorrhagic transformation of an ischemic stroke: Any extravascular blood within an area of known acute/subacute infarct, judged to be nontraumatic, without any related neurologic symptoms.

Criteria (must meet both of the following)

- 1) Imaging evidence (by CT or MR) of extravascular blood within the area of infarct.
- 2) No symptoms related to the hemorrhagic transformation.

Symptomatic intracerebral hemorrhage: Any extravascular blood in the brain parenchyma, judged to be nontraumatic, and not in the area of an acute/subacute ischemic infarct, associated with and identified as the predominant cause of new neurologic symptoms (including headache) or death. In the case of a mixed intracranial hemorrhage (Intracerebral Hemorrhage (ICH), Subarachnoid Hemorrhage (SAH), Subdural Hemorrhage (SDH) and/or Intraventricular Hemorrhage (IVH), the event should be classified according to the primary site of hemorrhage by the judgment of the clinician. For example, if a subject has a large ICH with a small amount of SAH, and the ICH is felt to be the primary site of bleeding, this should be classified as ICH.

Criteria: Evidence of hemorrhage in the brain parenchyma demonstrated by head imaging, surgery, or autopsy, which is not in the same territory of an underlying acute or subacute ischemic stroke, and is judged to be associated with any new neurologic symptoms (including headache) or leading to death.

Asymptomatic intracerebral hemorrhage: An acute extravasation of blood into the brain parenchyma, judged to be nontraumatic, and not in an area of an acute/subacute ischemic infarct, without associated neurologic symptoms or leading to death. In the case of a mixed intracranial hemorrhage (ICH, SAH, SDH and/or IVH), the event should be classified according to the primary site of hemorrhage by the judgment of the clinician.

For example, if a subject has a large ICH with a small amount of SAH, and the ICH is felt to be the primary site of bleeding, this should be classified as ICH.

Criteria: Evidence of hemorrhage in the brain parenchyma demonstrated by head imaging, surgery or autopsy, which is not in the same territory of an underlying acute or subacute ischemic stroke, and is not judged to be associated with any new neurologic symptoms or leading to death.

Other symptomatic intracranial hemorrhage: Any extravascular blood within the cranium judged to be nontraumatic, and the predominant cause of the clinical deterioration or that led to death. Other Intracranial Hemorrhage is defined as an acute extravasation of blood into the subarachnoid space, epidural space, subdural space or intraventricular space with associated symptoms (including headache). In the case of a mixed intracranial hemorrhage (ICH, SAH, SDH and/or IVH), the event should be classified according to the primary site of hemorrhage by the judgment of the clinician.

For example, if a subject has a large ICH with a small amount of SAH, and the ICH is felt to be the primary site of bleeding, this should be classified as ICH.

Criteria: Evidence of hemorrhage in the subarachnoid space, epidural space, or subdural space demonstrated by head imaging, surgery, or autopsy.

Other asymptomatic intracranial hemorrhage: An acute extravasation of blood into the subarachnoid space, epidural space, subdural space or intraventricular space without associated symptoms, and judged to be nontraumatic. In the case of a mixed intracranial hemorrhage (ICH, SAH, SDH and/or IVH), the event should be classified according to the primary site of hemorrhage by the judgment of the clinician. For example, if a subject has a large ICH with a small amount of SAH, and the ICH is felt to be the primary site of bleeding, this should be classified as ICH.

Criteria: Evidence of hemorrhage in the subarachnoid space, epidural space, or subdural space demonstrated by head imaging, surgery, or autopsy.

Myocardial infarction with coronary revascularization: Evidence of myocardial necrosis in a clinical setting consistent with myocardial ischemia, treated with coronary revascularization, such as angioplasty/stenting or coronary artery bypass graft (CABG), within 14 days.

Criteria: The diagnosis of MI will be based on an algorithm developed from the Universal Definition of Myocardial Infarction (Circulation 2007 116:2634-2653) that takes into account 5 categories of clinical information from the acute event: rise and/or fall of cardiac biomarkers, ECG abnormalities, clinical setting, imaging evidence, and pathology.

Myocardial infarction without coronary revascularization: Evidence of myocardial necrosis in a clinical setting consistent with myocardial ischemia, not treated with coronary revascularization within 14 days.

Criteria: The diagnosis of MI will be based on an algorithm developed from the Universal Definition of Myocardial Infarction (Circulation 2007 116:2634-2653) that takes into account 5 categories of clinical information from the acute event: rise and/or fall of cardiac biomarkers, ECG abnormalities, clinical setting, imaging evidence, and pathology.

Coronary revascularization without myocardial infarction: A procedure to improve coronary blood flow for documented coronary artery disease, but with no documentation of new post-randomization myocardial infarction.

Criteria: Documented coronary angioplasty, stenting, or bypass surgery for demonstrated or presumed coronary artery disease.

Major hemorrhage other than intracranial hemorrhage (life-threatening or non-life-threatening): A hemorrhagic event, judged to be nontraumatic, that results in intraocular bleeding causing loss of

vision, the need for a transfusion of two or more units of red cells or the equivalent amount of whole blood, or the need for hospitalization or prolongation of existing hospitalization [24]. This may include bleeding events related to surgical procedures but not those related to accidental trauma. Life-threatening hemorrhagic events will be defined as those that are fatal or require use of intravenous inotropic medication to maintain blood pressure, interventional treatment (including surgical, endoscopic or endovascular interventions), or transfusion of four or more units of red cells or the equivalent amount of whole blood. Non-life-threatening hemorrhagic events will be defined as those classified as major hemorrhagic events but not as life-threatening.

Minor hemorrhage other than intracranial hemorrhage: All hemorrhagic events leading to interruption or discontinuation of the study drug but not classifiable as major hemorrhagic events [24]. This may include bleeding events related to surgical procedures but not those related to accidental trauma.

Ischemic vascular death: Death due to ischemic stroke, myocardial infarction, sudden cardiac death, arrhythmia, pulmonary embolism, bowel or limb infarction, or any death not readily attributable to a non-ischemic cause.

Hemorrhagic Vascular death: Death due to intracranial or systemic hemorrhage.

Other Serious Adverse Event: Any adverse event, not belonging to the other outcome event categories, that is fatal or life threatening, is permanently or substantially disabling, requires or prolongs hospitalization, results in a congenital anomaly, or requires intervention to prevent permanent impairment or damage.

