## 12.5.2. Tertiary Analyses (given sufficient number of events, >15 events in total for both treatment arms, are available for analyses to be meaningful)

- Composite of ischemic stroke, MI, all-cause death, or major hemorrhage
- Composite ischemic stroke, TIA, MI, or ischemic vascular death
- TIA (as outcome)

- Coronary Revascularization
- Vascular death
- SAEs together and by major class (MedDRA Body System)
- New handicap/disability defined as 90 day mRS (>=2)
- 90 day mRS (ordinal)
- Asymptomatic intracranial hemorrhage (ICH, SAH, SDH or IVH)

These analyses are used to confirm or support the findings based on the primary outcome analysis. If most of the secondary outcomes show a change in the opposite direction from the primary or no change, we might have less confidence in the primary outcome.

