### **Table A.3 Coding of Composite Outcomes**

| webDCU
Code
Group
556 | Major Hemorrhage   | Hemorrhagic stroke  | Major Hemorrhage other
than Intracranial Hemorrhage
(a.k.a. Major systemic hemorrhage) | Coronary
Revascularization                                     | Ischemic
stroke   | Asymptomatic
intracranial
hemorrhage (ICH,
SAH, SDH or IVH) | All minor hemorrhage
(including
asymptomatic
intracranial
hemorrhage) |
|--------------------------------|--|---|--|---|--|--|---|
| 1                              |  |   |  |   | Ischemic stroke  |  |   |
| 2                              | Symptomatic hemorrhagic transformation of an ischemic stroke | Symptomatic hemorrhagic
transformation of an ischemic
stroke (OF INDEX EVENT OR
FOLLOW-UP EVENT) |  |   | Symptomatic hemorrhagic
transformation of an
ischemic stroke (NOT OF
INDEX EVENT)     |  |   |
| 3                              |  |   |  |   | Asymptomatic
hemorrhagic
transformation of an
ischemic stroke (NOT OF
INDEX EVENT) |  |   |
| 4                              | Symptomatic intracerebral hemorrhage                         | Symptomatic intracerebral hemorrhage  |  |   |  |  |   |
| 5                              |  |   |  |   |  | Asymptomatic intracerebral hemorrhage                                | Asymptomatic intracerebral hemorrhage   |
| 6                              | Other Symptomatic intracranial hemorrhage                    | Other Symptomatic intracranial hemorrhage If  |  |   |  |  |   |
| 7                              |  |   |  |   |  | Other Asymptomatic intracranial hemorrhage                           | Other Asymptomatic intracranial hemorrhage  |
| 9                              |  |   |  | Myocardial infarction
with Coronary
Revascularization       |  |  |   |
| 10                             |  |   |  |   |  |  |   |
| 11                             |  |   |  | Coronary
Revascularization
without Myocardial
Infarction |  |  |   |
| 12                             | Major Hemorrhage other
than Intracranial
Hemorrhage    |   | Major Hemorrhage other than
Intracranial Hemorrhage                                       |   |  |  |   |
| 13                             |  |   |  |   |  |  | Minor hemorrhage
other than intracranial
hemorrhage                         |

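### Read literally, the tertiary Coronary Revascularization outcome omits a first procedure done more than 14 days after a post-randomization MI

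*Protocol*

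**What the plan says.** Protocol 4.6.1 sets up three coronary categories.

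- MI with coronary revascularization is an MI "treated with coronary revascularization, such as angioplasty/stenting or coronary artery bypass graft (CABG), within 14 days".
- MI without coronary revascularization is an MI "not treated with coronary revascularization within 14 days".
- Coronary revascularization without MI is defined as a flow-restoring procedure for known coronary disease, "but with no documentation of new post-randomization myocardial infarction". Its separate criteria line reads "Documented coronary angioplasty, stenting, or bypass surgery for demonstrated or presumed coronary artery disease" and does not mention MI.

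Protocol 8.5.5 sends the same three categories to the cardiology/internal medicine adjudicators and adds no other coronary category.

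SAP 12.5.2 lists "Coronary Revascularization" among the tertiary outcomes without further definition. The tertiary analyses are run only if more than 15 events occur across both arms. SAP Table A.3 supplies the coding. Its Coronary Revascularization column has two entries: code 9, "Myocardial infarction with Coronary Revascularization", and code 11, "Coronary Revascularization without Myocardial Infarction". Row 10 has no entry in any column shown.

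**The concern.** The two codes that feed the outcome handle time differently. Code 9 takes procedures up to 14 days after the MI. Code 11 shuts out anyone with a documented MI at any time since randomization. A procedure that comes too late for code 9 is not passed on to code 11, so it falls between them.

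What is at stake is whether the outcome measures what its name says. As written, a first procedure in a subject with a trial MI counts or not according to its timing, whereas in a subject without a trial MI it counts whenever it happens. Because the tertiary analysis has a minimum event count, missed procedures also bear on whether it is run.

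**Working it through.** The plan gives no figure for this outcome, so there is none to reproduce. The check is to take each combination of post-randomization MI and first coronary procedure, apply the 4.6.1 definitions, and then read the Table A.3 column.

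| Case | Code 9 (procedure within 14 days of MI) | Code 11 (no documented post-randomization MI) | In the outcome? |
|---|---|---|---|
| (a) No trial MI, procedure | no | yes | yes |
| (b) MI, procedure within 14 days | yes | no | yes |
| (c) MI, no procedure | no | no | no, correctly |
| (d) MI, first procedure after more than 14 days | no, on timing | no, on the documented MI | no |

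Case (d) is the gap. An example is an MI on day 10 and bypass surgery on day 30. The interval is 30 − 10 = 20 days, so the MI is classed as MI without revascularization, and the surgery cannot take the code 11 definition because an MI is on record.

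Three limits on case (d):

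- It concerns a first procedure. A subject who also has a procedure before the MI, or within 14 days of it, already counts through code 11 or code 9.
- With follow-up to day 90 (SAP 4), the MI has to occur before day 90 − 14 = 76.
- Reading the blank row 10 as MI without revascularization is an inference from the code order. The result does not need it, because no third code enters the column.

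Scale, partly by assumption:

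- The emergency-department cohort in protocol 2.6 had 24 MI hospitalizations among 1,707 patients in 90 days: 24 / 1,707 = 1.4%.
- Applied to the 5,840 planned subjects: 5,840 × 24 / 1,707 ≈ 82 MIs.
- The share with a first procedure after day 14 but by day 90 is not in the documents. Assuming 2%: 0.02 × 82 ≈ 2 procedures. Assuming 15%: 0.15 × 82 ≈ 12 procedures.

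**The case against.** The strongest reply is that the event need not disappear. Protocol 4.6.1 has a residual category, Other Serious Adverse Event, for events outside the named categories that, among other things, require hospitalization. A day-30 bypass would qualify, and SAP 12.5.2 analyses SAEs overall and by class. This stands: the procedure misses one outcome, not every category. It does not close the gap, because no SAE code feeds the Coronary Revascularization column.

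Second, the code 11 criteria line carries no MI exclusion, so an adjudicator working from that line could assign code 11. The Manual of Procedures, which holds the detailed adjudication process, is not available here and might settle it. This also stands in part: the omission follows from the written definition and is not a certainty about practice. But the category title and the definition both exclude the event, and text that lets two adjudicators reach different answers needs clarifying in any case.

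Third, the threshold of more than 15 events is unlikely to turn on these procedures. If about 20% of the 82 MIs were revascularized promptly (16 / 82 = 19.5%), code 9 alone would pass it. The documents give no expected counts for code 9 or code 11, so the threshold adds little to the point.

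A reader might also infer that delays beyond 14 days are likely because protocol 7.4.1 stops study drug 5 days before an intervention. Five days fits well inside 14, so that section does not support the inference.

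**Conclusion.** The mismatch is real and minor. Under protocol 4.6.1 and SAP Table A.3 as written, a first coronary revascularization more than 14 days after a post-randomization MI is left out of the tertiary Coronary Revascularization outcome. The number cannot be derived from the documents; about 2 to 12 rests on the historical MI rate carrying over and on an assumed late share of 2% to 15%.

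The effect stops at one of nine tertiary outcomes. The MI itself still counts in the primary composite and as a secondary outcome, and the safety outcomes and stopping rules are untouched.

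Two stronger readings are not supported. A reader might infer that the treatment comparison is biased, since the omission falls on subjects who had an MI. The definitions are the same in both arms and are applied blinded, MIs treated within 14 days are counted, and nothing in the documents shows a difference between arms. A reader might also infer that an MI on day 85 with a procedure on day 95 is counted on the MI date. No section gives a dating rule for this outcome; the one in SAP 12.1.3 is written for the primary outcome. The date is unspecified, which is a reason to state it.

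**What to change.** Make two wording changes.

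1. In protocol 4.6.1, limit the code 11 exclusion to an MI within the preceding 14 days, and bring the category title, the criteria line and the list in 8.5.5 into agreement. Alternatively, keep code 11 as it is, add a category for a first procedure more than 14 days after an MI, and enter it in the Coronary Revascularization column of Table A.3.
2. In SAP 12.5.2 and Table A.3, state that the outcome is any coronary angioplasty, stenting or bypass from randomization to day 90, with or without an earlier trial MI, dated by the procedure.

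The cost is a blinded check of already reported MI and SAE records for late procedures, with adjudication of any found, and confirmation that the procedure date is available for code 9 events. The SAP is already at Version 8 (September 2017), so this should be done before database lock and code breaking, the point by which protocol 10.1 requires the final SAP. MI coding and the primary outcome do not change.
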